7.5 Withdrawal of informed consent for donated biological samples

If a volunteer withdraws consent to the use of donated biological samples, the samples will be disposed of/destroyed, and the action documented. If samples are already analyzed, AstraZeneca is not obliged to destroy the results of this research.

As collection of the biological samples is an integral part of the study, then the volunteer is withdrawn from further study participation.

The Investigator:

- Ensures volunteer's withdrawal of informed consent to the use of donated samples is notified immediately to AstraZeneca
- Ensures that biological samples from that volunteer, if stored at the study site, are immediately identified, disposed of /destroyed, and the action documented
- Ensures the laboratory(ies) holding the samples is/are informed about the withdrawn consent immediately and that samples are disposed/destroyed, the action documented, and the signed document returned to the study site
- Ensures that the volunteer and AstraZeneca are informed about the sample disposal.

AstraZeneca ensures the laboratory(ies) holding the samples is/are informed about the withdrawn consent immediately and that samples are disposed of/destroyed and the action documented and returned to the study site.

8. ETHICAL AND REGULATORY REQUIREMENTS

8.1 Ethical conduct of the study

The study will be performed in accordance with ethical principles that have their origin in the Declaration of Helsinki and are consistent with International Conference on Harmonization (ICH)/Good Clinical Practice (GCP), applicable regulatory requirements and the AstraZeneca policy on Bioethics and Human Biological Samples.

8.2 Subject data protection

The informed consent form will incorporate (or, in some cases, be accompanied by a separate document incorporating) wording that complies with relevant data protection and privacy legislation.

8.3 Ethics and regulatory review

An Institutional Review Board (IRB) should approve the final CSP, including the final version of the informed consent form and any other written information and/or materials to be provided to the volunteers. The Investigator will ensure the distribution of these documents to the applicable IRB, and to the study site staff.

The opinion of the IRB should be given in writing. The Investigator should submit the written approval to AstraZeneca before enrollment of any volunteer into the study.

The IRB should approve all advertising used to recruit volunteers for the study.

AstraZeneca should approve any modifications to the informed consent form that are needed to meet local requirements.

If required by local regulations, the CSP should be reapproved by the IRB annually.

Before enrollment of any volunteer into the study, the final CSP, including the final version of the informed consent form, is approved by the national regulatory authority or a notification to the national regulatory authority is done, according to local regulations.

AstraZeneca will handle the distribution of any of these documents to the national regulatory authorities.

AstraZeneca will provide Regulatory Authorities, IRBs, and Investigators with safety updates/reports according to local requirements, including suspected unexpected serious adverse reactions, where relevant.

The Investigator is responsible for providing the IRB with reports of any serious and unexpected adverse drug reactions from any other study conducted with the IP. AstraZeneca will provide this information to the Investigator so that he/she can meet these reporting requirements.

8.4 Informed consent

The Investigator will:

- Ensure each volunteer is given full and adequate oral and written information about the nature, purpose, possible risk, and benefit of the study
- Ensure each volunteer is notified that they are free to discontinue from the study at any time
- Ensure that each volunteer is given the opportunity to ask questions and allowed time to consider the information provided
- Ensure each volunteer provides signed and dated informed consent before conducting any procedure specifically for the study
- Ensure the original, signed informed consent form(s) is/are stored in the Investigator's Study File
- Ensure a copy of the signed informed consent form is given to the volunteer
- Ensure that any incentives for volunteers who participate in the study as well as any provisions for volunteers harmed as a consequence of study participation are described in the informed consent form that is approved by an IRB.

8.5 Changes to the protocol and informed consent form

Study procedures will not be changed without the mutual agreement of the Investigator and AstraZeneca.

If there are any substantial changes to the CSP, then these changes will be documented in a CSP amendment and where required in a new version of the CSP (Revised CSP).

The amendment is to be approved by the relevant IRB and if applicable, also the national regulatory authority, before implementation. Local requirements are to be followed for revised CSPs.

AstraZeneca will distribute any subsequent amendments and new versions of the CSP to the Investigator. For distribution to the IRB see Section 8.3.

If a CSP amendment requires a change to a center's informed consent form, AstraZeneca and the center's IRB are to approve the revised informed consent form before the revised form is used.

If local regulations require, any administrative change will be communicated to or approved by the IRB.

8.6 Audits and inspections

Authorized representatives of AstraZeneca, a regulatory authority, or an IRB may perform audits or inspections at the center, including source data verification. The purpose of an audit or inspection is to systematically and independently examine all study-related activities and documents, to determine whether these activities were conducted, and data were recorded, analyzed, and accurately reported according to the CSP, GCP, guidelines of the ICH, and any applicable regulatory requirements. The Investigator will contact AstraZeneca immediately if contacted by a regulatory agency about an inspection at the center.

9. STUDY MANAGEMENT BY ASTRAZENECA

9.1 Prestudy activities

Before the first volunteer is entered into the study, it is necessary for a representative of AstraZeneca to visit the investigational study site to:

- Determine the adequacy of the facilities
- Determine availability of appropriate volunteers for the study
- Discuss with the Investigator(s) (and other personnel involved with the study) their responsibilities with regard to CSP adherence, and the responsibilities of AstraZeneca or its representatives. This will be documented in a CSA between AstraZeneca and the Investigator.

9.2 Training of study site personnel

Before the first volunteer is entered into the study, an AstraZeneca representative will review and discuss the requirements of the CSP and related documents with the investigational staff and also train them in any study-specific procedures and system(s) utilized.

The Investigator will ensure that appropriate training relevant to the study is given to all of these staff, and that any new information relevant to the performance of this study is forwarded to the staff involved.

The Investigator will maintain a record of all individuals involved in the study (medical, nursing, and other staff).

9.3 Monitoring of the study

During the study, an AstraZeneca representative will have regular contacts with the study site, including visits to:

- Provide information and support to the Investigator(s)
- Confirm that facilities remain acceptable
- Confirm that the investigational team is adhering to the CSP, that data are being accurately and timely recorded in the eCRFs, that biological samples are handled in accordance with the Laboratory Manual, and that IP accountability checks are being performed
- Perform source data verification (a comparison of the data in the eCRFs with the volunteer's medical records at the hospital or practice, and other records relevant to the study) including verification of informed consent of participating volunteers. This will require direct access to all original records for each volunteer (eg, clinic charts)
- Ensure withdrawal of informed consent to the use of the volunteer's biological samples is reported and biological samples are identified and disposed of/destroyed accordingly, and the action is documented, and reported to the volunteer.

The AstraZeneca representative will be available between visits if the Investigator(s) or other staff at the center needs information and advice about the study conduct.

Source data

Refer to the CSA for location of source data.

9.4 Study agreements

The Investigator at the center should comply with all the terms, conditions, and obligations of the CSA, or equivalent, for this study. In the event of any inconsistency between this CSP and

the CSA, the terms of CSP shall prevail with respect to the conduct of the study and the treatment of volunteers and in all other respects, not relating to study conduct or treatment of volunteers, the terms of the CSA shall prevail.

Agreements between AstraZeneca and the Investigator should be in place before any study-related procedures can take place, or volunteers are enrolled.

Archiving of study documents

The Investigator follows the principles outlined in the CSA.

9.5 Study timetable and end of study

The end of the study is defined as ‘the last visit of the last volunteer undergoing the study’.

The study is expected to start in Quarter 3 2013 and to end by Quarter 1 2014.

The study may be terminated at the center if the study procedures are not being performed according to GCP, or if recruitment is slow. AstraZeneca may also terminate the entire study prematurely if concerns for safety arise within this study or in any other study with AZD9291.

10. DATA MANAGEMENT BY QUINTILES

Data management will be performed by [REDACTED]. A 21 Code of Federal Regulations part 11-compliant EDC system will be used for this study. Electronic CRFs will be produced by [REDACTED] for each volunteer.

The data collected through third party sources will be obtained and reconciled against study data.

Adverse events and medical/surgical history will be classified according to the terminology of the latest version the Medical Dictionary for Regulatory Activities (MedDRA). Medications will be classified according to the AstraZeneca Drug Dictionary. All coding will be performed by [REDACTED].

Data queries will be raised for inconsistent, impossible, or missing data. All entries to the study database will be available in an audit trail.

The data will be validated as defined in the Data Management Plan. Quality control procedures will be applied to each stage of data handling to ensure that all data are reliable and have been processed correctly.

When all data have been coded, validated, signed, and locked, clean file will be declared. Any treatment-revealing data may thereafter be added and the final database will be locked.

11. EVALUATION AND CALCULATION OF VARIABLES

11.1 Calculation or derivation of safety variable(s)

11.1.1 Calculation of change from baseline

Change-from-baseline variables will be calculated for the safety variables listed below, as the posttreatment value minus the value at baseline. The baseline values will be as follows:

- Clinical laboratory tests: Day -1 of Period 1
- Vital signs: Day 1 predose of Period 1
- ECG: Day 1 predose of Period 1

If a volunteer is missing the baseline collection, the previous nonmissing evaluation will become the baseline value. If no baseline or previous-to-baseline evaluations exist, then the baseline value will be treated as missing and no change-from-baseline value will be calculated.

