This is a Phase 1, open-label, 2-part (Part A and Part B) study. Part A will be conducted as a 3-period, non-randomized sequential design in which healthy male volunteers will receive single 20-mg doses of AZD9291 as a capsule in Period 1, as a solution in Period 2, and as a tablet in Period 3, all in the fasted state. Part B will be conducted as a 2-period, fixed-sequence design in which a separate cohort of healthy male volunteers will receive a single 20-mg dose of AZD9291 under fasted conditions in Period 1, and under fed conditions (following a high-fat breakfast) in Period 2. The results from Part A will determine whether the 20-mg capsule formulation or the 20-mg tablet formulation will be selected for assessment of the food-effect in Part B. There will be a minimum of a 21-day washout between each dose in both study parts.

Target subject population

The target population is healthy male volunteers between the ages of 18 and 55 years, inclusive, with a body mass index between 19.0 and 30.0 kg/m² and body weight at least 50 kg and no more than 100 kg.

Investigational product, dosage, and mode of administration

During each treatment period of Part A, a single dose of 20-mg AZD9291 will be administered in the fasted state as either a capsule formulation, as a solution formulation, or as a tablet formulation, with 240 mL of water. In Part B, a single dose of either the 20-mg AZD9291 capsule or tablet formulation will be administered in both the fasted and fed state. The selection of the formulation for Part B will depend on the relative bioavailability results of Part A.

Comparator, dosage, and mode of administration

None

Duration of treatment

Part A

The duration of volunteer participation will be approximately 14 weeks. This includes a 28-day screening period, 3 treatment periods, and a final follow-up visit. There will be a minimum of 21-day washout between doses in each treatment period. A final post-study visit will take place between 21 and 28 days after the last dose of AZD9291 (up to 7 days after completion of Period 3). During the study, each volunteer will receive single, 20-mg doses of AZD9291 on 3 separate occasions.

Part B

The duration of volunteer participation will be approximately 11 weeks. This includes a 28-day screening period, 2 treatment periods separated by a 21-day washout between doses, and a final follow-up visit. A final post-study visit will take place between 21 and 28 days

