after the last dose of AZD9291 (up to 7 days after completion of Period 2). During the study, each volunteer will receive a single, 20-mg dose of AZD9291 on 2 separate occasions.

Outcome variable(s):

- Pharmacokinetics
 - AZD9291 and AZ5104 and AZ7550 (AZD9291 metabolites) plasma concentrations will be used to assess the following parameters, as applicable: AUC, AUC₍₀₋₇₂₎, AUC_(0-t), C_{max}, t_{1/2,λz}, λ_z, t_{max}, t_{lag}, CL/F (AZD9291 only), and V_z/F (AZD9291 only), and parent to metabolite ratio (calculated as AZD9291/AZ5104 and AZD9291/AZ7550 for both C_{max} and AUC) (Part A and Part B).
 - The primary variables for assessments of relative bioavailability are AZD9291 C_{max}, AUC, and/or AUC_(0-t) (Part A).
 - The secondary variable for assessment of relative bioavailability is t_{max} (Part A).
 - The primary variables for assessment of food-effect are AZD9291 C_{max}, AUC, and/or AUC_(0-t) (Part B).
 - The secondary variable for assessment food-effect is t_{max} (Part B).
- Safety (secondary endpoints)

Safety parameters include adverse events, vital signs, physical examinations, ophthalmologic examination, electrocardiograms, and clinical laboratory assessments (Part A and Part B).

Statistical methods

Part A

Inferential statistical analyses will be performed on the pharmacokinetic data only. The bioavailability of the 20-mg solution and a 20-mg tablet relative to the 20-mg capsule will be assessed using the primary pharmacokinetic variables, C_{max}, AUC, and/or AUC_(0-t), of plasma AZD9291. These endpoints will be natural log-transformed and analyzed using a linear mixed effects model. The difference in treatment (formulation) means will be determined along with its associated 90% confidence interval and back-transformed to give an estimate of the relative bioavailability. The results of this analysis will be presented in terms of geometric means for each treatment, the relative bioavailability (ie, the ratio of the treatment formulation geometric means) and its 90% confidence interval.

The above treatment comparisons will also be performed for t_{max} as the secondary analyses. Nonparametric methods will be used to compute median t_{max} for each treatment, median t_{max} difference, and associated 90% confidence interval for the median difference. The data will

be analyzed by a Wilcoxon Signed-Rank Test. The 90% confidence interval will be calculated using the method of Hahn and Meeker (Hahn and Meeker 1991).

Part B

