- h The follow-up visit may coincide with the Period 2 Day 22 assessment; in this case, only 1 set of assessments is needed.
- i Serious AEs will be collected beginning at informed consent; nonserious AEs will be collected beginning at the first intake of IP.
- j Includes clinical chemistry, hematology, and urinalysis at screening, Day -1, Day 3, Day 8, Day 15, Day 22, and at follow-up; see Table 7 for time points and specific tests to be performed.

Table 3 Schedule of assessments for each treatment period (Part A)

Time (hours) relative to dose	Supine pulse and blood pressure	ECG 12-lead	Safety blood and urine	PK blood	Food and fluid	Resident
Predose	X	X		X ^a		↓
Dosing					D	
0.5				X		
1	X	X		X	F ^b	
1.5				X		
2	X	X		X		
3				X		
4	X	X		X	M ^b	
6				X		
8	X	X		X		
10				X		
12	X	X		X		
24 (Day 2)	X	X		X		
48 (Day 3)	X	X	X	X		
72 (Day 4)				X		
120 (Day 6)				X		
168 (Day 8)	X	X	X	X		
216 (Day 10)				X		
336 (Day 15)	X	X	X	X		
504 (Day 22) ^c	X	X	X	X		

D drink, consisting of 240 mL water; F free access to fluids; M meal.

ECG electrocardiogram, PK pharmacokinetics

^a Predose sample must be collected within the 30 minutes prior to dosing.

^b Water can be allowed as desired, except for 1 hour before and after drug administration (apart from the 240 mL water given with the dose). No food should be allowed for at least 4 hours postdose. A standard meal will be given 4 hours postdose after completion of all simultaneously scheduled study procedures.

^c The Day 22 postdose assessments in Periods 1 and 2 may be the same as the timing of the predose assessments in Periods 2 and 3, respectively, if a 21-day washout is used. In this case, only 1 set of assessments needs to be collected, which are the predose assessments scheduled for Day 1 of the following period.

Table 4 Schedule of assessments for each treatment period (Part B)

Time (hours) relative to dose	Supine pulse and blood pressure	ECG 12-lead	Safety blood and urine	PK blood	Food and fluid	Resident
Predose	X	X		X ^a	Breakfast ^b	↓
Dosing					D	
0.5				X		
1	X	X		X	F ^c	
1.5				X		
2	X	X		X		
3				X		
4	X	X		X	M ^c	
6				X		
8	X	X		X		
10				X		
12	X	X		X		
24 (Day 2)	X	X		X		
48 (Day 3)	X	X	X	X		
72 (Day 4)				X		
120 (Day 6)				X		
168 (Day 8)	X	X	X	X		
216 (Day 10)				X		
336 (Day 15)	X	X	X	X		
504 (Day 22) ^d	X	X	X	X		

D drink, consisting of 240 mL water; F free access to fluids; M meal.

ECG electrocardiogram, PK pharmacokinetics

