12.2.3 Safety

All safety data (scheduled and unscheduled) will be presented in the data listings.

Safety variables (eg, clinical laboratory values and vital signs) will be reported to the same precision as the source data. Derived variables will be reported using similar precision to those from which they were derived (eg, QTcF derived from QT interval).

Extra measurements (such as unscheduled or repeat assessments) will not be included in the descriptive statistics by scheduled time point, but will be included in data listings. All AEs and clinical laboratory outliers that occur following the first dose of study medication will be included in the tabulations of AEs and outlier events, including episodes that occur at unscheduled evaluations.

All available data from volunteers in the safety analysis set will be included in the safety analyses. No adjustment or imputation will be utilized for missing values or for volunteers who withdraw prior to completing the study, neither will analyses be restricted to volunteers with complete data.

Adverse events beginning at or after the first dose of IP will be summarized by preferred term and system organ class using MedDRA vocabulary by treatment and across all treatments. Adverse events that begin during the washout periods will be assigned to the last treatment received prior to the onset of the AE. Furthermore, listings of SAEs and AEs that lead to withdrawal will be made and the number of volunteers who have any AEs, SAEs, AEs that lead to withdrawal, and AEs with severe intensity will be summarized.

Tabulations and listings of data for vital signs, clinical laboratory tests, ECGs, and physical and ophthalmologic examination findings will be presented, as appropriate. All continuous safety data will be summarized by treatment and/or across all treatments, as appropriate, for the observed value at each scheduled assessment and for the corresponding change from baseline. For clinical laboratory tests, listings of values for each volunteer will be presented with abnormal or out-of-range values flagged. Clinical laboratory data will be reported in Système International units in the CSR.

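### Safety change from baseline always refers to Period 1, so by-treatment columns for the later doses carry in change from earlier periods (minor)

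*Protocol*

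**What the plan says.** Section 11.1.1 of the protocol defines change "as the posttreatment value minus the value at baseline" and gives one baseline for each type of measurement, always in Period 1:

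- "Clinical laboratory tests: Day -1 of Period 1"
- "Vital signs: Day 1 predose of Period 1"
- "ECG: Day 1 predose of Period 1"

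No period-specific baseline is defined. Section 12.2.3 then states: "All continuous safety data will be summarized by treatment and/or across all treatments, as appropriate, for the observed value at each scheduled assessment", and the same sentence adds the corresponding change from baseline.

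Section 3.1 fixes the order: capsule, solution, tablet in Part A; fasted, then fed in Part B. On spacing, the synopsis says: "There will be a minimum of a 21-day washout between each dose in both study parts".

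Tables 3 and 4 schedule predose vital signs and ECG in every period. The footnotes to the overall study plans place laboratory tests on Day -1, and allow one shared Day 22/predose set if the washout is exactly 21 days.

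**The concern.** In a by-treatment table with a Period 1 baseline, the change shown for the tablet is everything that has happened since before the capsule. That covers any response to the tablet, but also the passage of time, repeated blood sampling and whatever remains of two earlier doses. The solution and fed columns carry one earlier period in the same way. The capsule and fasted columns carry none, so columns set side by side measure change over different spans.

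Two features of the plan make this more than a formality. Section 12.2.3 assigns an adverse event in washout to the last treatment received, while the measured safety variables in the same section refer back to before the first treatment. Also, ECG and vital signs are recorded at 1 to 12 hours after each dose, and Section 1.3.2 reports nonclinical QT, heart-rate and blood-pressure findings. For an acute postdose change, the same-day predose value is the closer reference, and it is already collected.

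At stake is how clearly descriptive safety tables for the later treatments can be read. No pharmacokinetic result depends on it.

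**Working it through.** **1. Reproducing the protocol's blood volume (Table 8, Part A).** 16 × 8.5 + 16 × 4 + 8.5 + 57 × 2 + 39 × 1 = 136 + 64 + 8.5 + 114 + 39 = 361.5 mL, as stated.

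Rebuilt from the schedule:

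- Each period has 19 PK samples (2 mL each), 13 of them up to 48 h (1 mL catheter discard each), and 5 laboratory draws (Days -1, 3, 8, 15, 22) of 8.5 + 4 = 12.5 mL.
- Per period: 5 × 12.5 + 19 × 2 + 13 = 62.5 + 38 + 13 = 113.5 mL.
- Screening: 12.5 + 8.5 (serology) = 21 mL.
- Total: 21 + 3 × 113.5 = 361.5 mL, which agrees.

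**2. Age of the baseline.** With the minimum washout, the baseline in period p is 21 × (p − 1) days old at dosing and 21 × p days old at Day 22.

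| Period | Treatment | At dosing | At Day 22 |
|---|---|---|---|
| 1 | capsule; fasted | 0 weeks | 3 weeks |
| 2 | solution; fed | 3 weeks | 6 weeks |
| 3 | tablet | 6 weeks | 9 weeks |

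**3. Blood drawn from the baseline sample onward, up to the later period's own predose laboratory sample.** Screening blood is left out because it is drawn before the baseline.

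- Separate Day 22 and Day -1 laboratory draws: 113.5 mL per earlier period, so 113.5 mL before Period 2 and 227 mL before Period 3.
- Shared Day 22/predose laboratory set: 4 × 12.5 + 38 + 13 = 101 mL per earlier period, so 101 and 202 mL.
- If no catheter is used, 13 mL per period drops out: 101 − 13 = 88 mL and 2 × 88 = 176 mL for the shared set.

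The Part B figure uses the Table 4 schedule. Table 9 adds up to its stated 297.5 mL, but it lists 14 laboratory draws and 38 discards, where the schedule gives 11 to 12 and 26 (248 to 260.5 mL). Those counts should be reconciled separately.

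**4. Translation to haemoglobin.** The protocol gives no blood volume or haemoglobin level. Assumed: 4.5 to 6 L, 150 g/L and no regeneration, which makes these upper bounds.

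- 227 mL: 227/6000 = 3.8% to 227/4500 = 5.0%; × 150 = 5.7 to 7.6 g/L.
- 113.5 mL: 1.9% to 2.5%; × 150 = 2.8 to 3.8 g/L.

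**5. With a same-period baseline.** At Day 22 the baseline is 3 weeks old for every treatment. Blood drawn since baseline is about 101 to 114 mL for every treatment, against up to 227 mL (Period 2) and 3 × 113.5 = 340.5 mL (Period 3) under the present definition.

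**6. What a same-period baseline may itself carry.** The fraction remaining at 504 h is 0.5^(504/half-life), using the half-lives in Section 3.2:

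- AZ5104 (70 h): 0.7%
- AZ7550 (120 h): 5.4%
- AZD9291 (30 to 110 h): 0.001% to 4.2%

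**The case against.** The strongest reply is that the Period 1 baseline is the right one for the stated purpose. Section 2.2 asks for the safety and tolerability of AZD9291 in healthy volunteers. Section 3.2 concedes that 21 days is unlikely to clear the metabolites fully, and Section 1.1 calls the drug an irreversible inhibitor. Only the Period 1 value precedes all exposure; subtracting a later one could hide a persisting or cumulative effect. This stands, and it is why the Period 1 baseline must be kept.

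A reader might infer that the safety objective compares formulations or fed with fasted dosing, or that drift will be reported as an effect of the named treatment. The documents support neither. Section 2.2 contains no such comparison; the synopsis says "Inferential statistical analyses will be performed on the pharmacokinetic data only"; and 12.2.3 is descriptive, may pool treatments, and shows observed values from which a carried-in offset can be read.

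The fixed-order limitation is also acknowledged. In the synopsis the caveat follows directly on the sentence about descriptive summaries of all other data, so it can be read as covering safety. In Section 12, however, it appears only under pharmacokinetics (12.2.4).

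Finally, a statistical analysis plan, which is not at hand, could add the display within the latitude that 12.2.3 leaves. That lowers the weight of the point, but 11.1.1 as written fixes a single baseline.

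**Conclusion.** The point holds as a minor one. Under 11.1.1 and 12.2.3 together, by-treatment change for the solution, the fed dose and the tablet includes change carried in from earlier periods, although the values needed to remove it are already collected.

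The only part that can be sized from the protocol is blood loss, which mainly concerns haematology: about 101 to 114 mL before Period 2 and 202 to 227 mL before Period 3. The bound of about 6 to 8 g/L of haemoglobin for 227 mL rests on the assumed blood volume, haemoglobin level and absence of regeneration; the true shift would be smaller. The documents give no basis for sizing drift in vital signs, ECG or chemistry.

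Three stronger readings do not hold:

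- A baseline six or more weeks old at dosing applies to the tablet only.
- Counting all blood before Period 3 (21 + 227 = 248 mL) overstates the loss since baseline, because 21 mL is taken at screening.
- The Period 1 baseline is not what makes later changes hard to attribute. Treatment and period are completely confounded by the fixed order, and no choice of baseline alters that.

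**What to change.** - In 11.1.1, keep the Period 1 baseline for cumulative change. Add that, for summaries by treatment, change will also be calculated from the same period's own predose value: Day -1 laboratory tests, or the shared Day 22/predose set where that is used, and Day 1 predose vital signs and ECG. Note that a shared set then serves both as the last value of one period and as the baseline of the next.
- State that this addition concerns summaries only and leaves the increase-from-baseline discontinuation criteria in Sections 5.8 and 6.3.5 untouched.
- In 12.2.3, repeat the period-effect caveat that now stands in 12.2.4.

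The cost is a few sentences and one more set of change columns; no new sample or visit is needed. The downside is that the Period 2 and 3 baselines follow exposure and may carry residual drug or metabolite effect, which the retained Period 1 summary would show.
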